## 8.2.1.2. ICC (NL)

The Netherlands has a population of approximately 17.2 million inhabitants, with a UC prevalence of approximately 226 per 100000 population (de Groof et al., 2016) and an incidence of around 17.2/100000 person-years (PYs) (Ng et al., 2017). Patients with IBD are typically treated by a gastroenterologist (specialist).

All adult Dutch residents are obliged to purchase basic health insurance from a private firm. The basic package – based on an officially set premium – covers medical and dental care, hospitalization, and a variety of medical appliances, pharmaceuticals, and paramedical care.

Complementing insurance can be purchased by individuals to cover requirements beyond the basic package. Insurance companies are, however, free to set prices, and, unlike the basic package, can reject applicants.

In the ICC Registry, patients with IBD 16 years of age or older, with an established diagnosis of UC or Crohn's Disease (CD), are eligible. Follow-up visits after the initial baseline visit (Week 0) are scheduled on Week 12, 24, 52, and once yearly up to 10 years after initiation of treatment.

If a patient discontinues medication and initiates another treatment that is included in the ICC Registry, the follow-up is scheduled at Week 12, 24, 52, and once yearly.

Patients included in the study should be included in the registry at least 12 weeks prior to analyses.

In total, 20 hospitals are involved in ICC; these include all university hospitals in the Netherlands and multiple large non-university hospitals. Officially, there are 69 hospitals in the Netherlands; this number however includes a lot of small medical centers, which only have small numbers of patients with IBD and often do not prescribe second- or third-line biologics easily. Overall, with the 20 large hospitals that are involved in ICC, it is estimated that ICC covers at least 50% of patients with IBD in the Netherlands.

For more details on the ICC Registry, see Section 8.4.2.

#### 8.2.1.3. SWIBREG (SWE)

Sweden is a Scandinavian country with 10 million residents. Healthcare is publicly funded, and prescription drugs are provided free of charge above an annual threshold of approximately \$250 United States dollars (Laugesen et al., 2021).

Health and demographic information are recorded in a series of registers with a very high degree of completeness resulting from the mandatory and semiautomated registration. Based on each Swedish resident's unique personal identification number, issued to all Swedish residents alive in 1947 or born thereafter, linkage of data from different registers is possible (Ludvigsson et al., 2009). The registers are maintained by governmental bodies (the main registers used in this project are held by the National Board of Health and Welfare [Socialstyrelsen]) and Statistics Sweden, who may perform data linkages and provide de-identified data for research purposes (Laugesen et al., 2021). The UC incidence among Swedish adults for the years 2006 to 2013 was estimated as 20 per 100000 PYs (Everhov et al., 2018). By 2018 there were approximately 51000 prevalent patients with UC in Sweden (Olén et al., 2020), yielding a UC prevalence of approximately 500 per 100000 population.

Patients with UC are typically treated by gastroenterologists, the vast majority of whom work in public and hospital-based clinics. All patients who are to be included in this study are registered in SWIBREG (Ludvigsson et al., 2019). The linkage of this registry to other relevant nationwide registers enables monitoring of existing IBD therapies, as they are used in clinical practice.

By 2020, the SWIBREG database covered approximately 26000 patients with UC (Myrelid et al., 2021). Although the coverage is not complete, the coverage of moderate to severe UC in SWIBREG was 80-90% in 2020 and tended to be patchy (i.e. no or very poor coverage in some centers and close to complete coverage in most).

For more details on SWIBREG, see Section 8.4.3.

#### 8.2.2. Inclusion Criteria

Across all 3 registries, adult patients ( $\geq$ 18 years) of any sex with UC that are enrolled in 1 of the 3 IBD registries after 10 March 2023 and during the observational period (complying with the register's requirements for inclusion including patient consent) and initiated on filgotinib after 10 March 2023. Initiation is defined as either no prior filgotinib use or prior use that was discontinued before 10 March 2023 (thus, patients who are non-naïve to filgotinib can be included).

There are no restrictions on patient inclusion in terms of either historical data or minimum amount of follow-up.

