#### **Population:**

The study population will include consecutive adult patients ( $\geq 18$  years of age) of all sexes with prevalent or incident UC identified from 3 registries being initiated on filgotinib after the EC decision date on Article 20.

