## 8.2. Setting and Study Population

#### 8.2.1. IBD Registries

#### 8.2.1.1. ENEIDA (ES)

Spain's healthcare system guarantees universal coverage for all residents (N = 47 million) and is principally funded through taxation. Specialist care is provided in specialist care centers and hospitals in the form of outpatient and inpatient care.

Most hospitals in Spain have an electronic medical record (EMR) system that provides access for clinicians to review all care that takes place in the same hospital. Moreover, an increasing number of geographical areas have implemented an EMR system that allows access to all the information generated by public hospitals in the same region. Some also provide access to general practitioner data.

Patients with IBD will typically be followed by their gastroenterologist (specialist) in a hospital outpatient setting on a regular basis. For stable asymptomatic patients, follow-up will be scheduled to happen at least every 2 years, whereas for patients with active moderate to severe UC or with ongoing treatment with biologics, follow-up will happen at least every 6 months, based on clinical guidelines in Spain.

The UC prevalence in Spain has been estimated at around 88 per 100000 population (Marín-Jiménez et al., 2018), the annual incidence at 8.1 per 100000 individuals (Chaparro et al., 2021), which is in line with those reported in other European countries.

As of February 2023, there were 37865 patients with UC enrolled in the ENEIDA registry; between 2000 and 3000 additional patients with UC are enrolled annually in the registry. More than 20000 of the enrolled patients are from centers meeting the criteria for research-quality data. These figures indicate that ENEIDA currently covers about 10% of all existing cases of UC in Spain. However, the registry is likely to enroll a significantly larger proportion of all newly diagnosed patients with UC and of initiators of advanced therapies for UC in Spain.

For specific details on the ENEIDA registry, see Section 8.4.1.

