Furthermore, not all information that is relevant in the context of this DUS may be captured by all registries. For instance, in the context of skin malignancies (NMSC), none of the registries systemically records information on periodic skin examination. Therefore, this cannot be reliably followed or measured in any of the three registries used in this DUS. Moreover, not all registries capture the same information, nor is the process of data capturing the same. While e.g. in SWIBREG – due to data linkage to various other Swedish data sources and registries – the vast majority of variables will be available, in ENEIDA information on many variables will need to be extracted from EMRs.

The analyses of this DUS will be restricted to the period after the EC decision date on the JAKi Article 20 procedure (10 March 2023), and therefore not include filgotinib data of the pre-referral period. The rationale for this is that the number of patients identified in the registries exposed to filgotinib in the pre-referral period, i.e. between the filgotinib EU approval date (Netherlands: 12-Nov-2021; Spain: 01-May-2023 [= date of reimbursement approval of filgotinib in Spain on a national level]; Sweden: 12-Nov-2021) and the EC decision date is very limited (ICC: n=54; ENEIDA: n=19; SWIBREG n=44).

Any non-interventional study can suffer from bias, specifically, selection or information bias. However, this study aims to capture up to 500 consecutive patients per registry initiating filgotinib in the observational period. Therefore, this study will reflect the clinical practice and characteristics of these patients.

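### Section 8.2.2, as written, requires registry enrolment after 10 March 2023 as well as filgotinib initiation, which would exclude already-registered initiators and contradicts the population described elsewhere

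*Protocol*

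**What the plan says.** Section 8.2.2 of the protocol sets two dated conditions. Patients must be adults with UC "that are enrolled in 1 of the 3 IBD registries after 10 March 2023 and during the observational period", complying with the register's inclusion and consent requirements, "and initiated on filgotinib after 10 March 2023". It then defines initiation so that earlier use stopped before that date is allowed ("thus, patients who are non-naïve to filgotinib can be included") and says that inclusion is not restricted by historical data or minimum follow-up.

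Other sections describe the population without an enrolment date:

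- Abstract, Population: consecutive adults "with prevalent or incident UC identified from 3 registries being initiated on filgotinib after the EC decision date on Article 20".
- Section 8.1: up to 500 consecutive adults per registry who start filgotinib after the decision.
- Section 8.2.3: the only exclusion is filgotinib use that was ongoing at the decision date.
- Section 8.2.4: the index date is the filgotinib start.
- Section 8.5: up to 500 eligible initiators per registry.
- Section 8.9: "this study aims to capture up to 500 consecutive patients per registry initiating filgotinib in the observational period".

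**The concern.** The first condition in Section 8.2.2 reads as the act of enrolment, because it is qualified by registry inclusion requirements and consent. Sections 8.6.1 and 9.3.3 place consent at enrolment. On that reading, anyone already registered on 10 March 2023 is lost, however long after that date they start filgotinib.

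Two things are at stake. First, Section 8.9 answers the risk of selection bias by pointing to consecutive initiators. A cohort filtered on recent enrolment is not consecutive. Second, Section 8.9 names as its most important limitation that the study cannot reliably judge whether suitable alternatives existed, and it uses prior UC treatment as a partial substitute. Selecting on recent enrolment could distort that history, and possibly age and comorbidity.

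The ambiguity could also produce different cohorts. The abstract has each registry, or its local provider, run its own analysis, and Section 8.6.3 has an outside authority build the Swedish cohort. ENEIDA holds the date of inclusion in the registry as a critical variable (Section 8.4.1.2), so the literal filter can be programmed. One team could apply it while another does not.

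**Working it through.** **The plan's own figures.** The protocol does not say what share of filgotinib initiators were already enrolled. Its study-size figures in Section 8.5 reproduce: 3/0.01 = 300, and √(0.10 × 0.90/300) = 1.7%, giving a 95% CI of 6.6% to 13.4%. They are not in dispute.

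**Internal consistency.** Take a patient enrolled in 2019 who first starts filgotinib in 2024.

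- Abstract and Sections 8.1, 8.5 and 8.9: nothing removes this patient on enrolment date.
- Section 8.2.3: not excluded.
- Section 8.2.4: has a valid index date.
- Section 8.2.2, literally: ineligible.

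Now take a patient who used filgotinib in 2022, stopped, and restarts in 2024. Section 8.2.2 admits re-initiators. Section 8.9 counts the pre-decision users identified in the registries and says their number "is very limited (ICC: n=54; ENEIDA: n=19; SWIBREG n=44"), that is 54 + 19 + 44 = 117. Any of these who stopped and later restart would generally have been enrolled before the cut-off and would fail the enrolment condition. The allowance would then cover little beyond patients whose earlier use predates their registration.

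**Share of registered UC patients failing on enrolment date.** Formula: already enrolled / (already enrolled + 4 years of new enrolment).

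ENEIDA inputs:

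- Section 8.2.1.1: "As of February 2023, there were 37865 patients with UC enrolled in the ENEIDA registry", with 2,000 to 3,000 added a year, so 8,000 to 12,000 over 4 years. More than 20,000 are at research-quality centres.
- Section 8.4.1.1: more than 30,000 on active follow-up.

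| Base | 8,000 new | 12,000 new |
|---|---|---|
| 37,865 (all) | 37,865/45,865 = 83% | 37,865/49,865 = 76% |
| 30,000 (active follow-up) | 30,000/38,000 = 79% | 30,000/42,000 = 71% |
| 20,000 (research-quality centres, against all new enrolment) | 20,000/28,000 = 71% | 20,000/32,000 = 63% |

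**From registered patients to initiators.** New enrollees form the majority of initiators only if they start filgotinib at more than (already enrolled)/(new) times the rate of existing patients. On the first two bases this ratio runs from 30,000/12,000 = 2.5 to 37,865/8,000 = 4.7. On the 20,000 base it can be as low as 20,000/12,000 = 1.7. The protocol gives no initiation rates.

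**SWIBREG.** Section 8.2.1.3 gives about 26,000 UC patients by 2020 and an adult incidence of 20 per 100,000 person-years. Assume 8 to 10 million adults, all incident UC enrolled, and no catch-up of unregistered prevalent patients. New enrolment over 4 years is then 4 × 0.0002 × 8 million = 6,400, up to 8,000 with 10 million. The share is 26,000/32,400 = 80% down to 26,000/34,000 = 76%. This result depends on those assumptions.

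**ICC.** Patients enter when they start a novel drug (Sections 8.4.2 and 8.4.2.1), so first-time entrants on filgotinib qualify even under the literal rule. Mainly patients enrolled earlier on another drug would be lost (Section 8.2.1.2 describes such switchers). The protocol gives no count of them.

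**The case against.** The strongest reply is that the clause means registry membership during the study window. That is possible and probably what was intended. Section 8.2.2 itself admits re-initiators and disclaims limits on historical data. The operational sections apply no enrolment filter: ENEIDA reviews charts for all identified filgotinib users (Section 8.6.1), ICC includes all users from 2022 (Section 8.4.2), and the Swedish linkage steps contain no such step (Section 8.6.3). This bears on intent, but the governing eligibility sentence still does not say it.

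The reply also limits the conclusion:

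- A reader might infer that most filgotinib candidates would be excluded. The documents do not show this. The ENEIDA percentages are shares of registered UC patients, and Section 8.2.1.1 says ENEIDA probably captures a larger proportion of new diagnoses and of advanced-therapy initiators, so new enrollees may start filgotinib at a higher rate.
- A reader might take Section 8.2.1.3 ("the coverage of moderate to severe UC in SWIBREG was 80-90% in 2020") as the share of Swedish initiators already enrolled. It is a coverage figure from 2020, described there as patchy.
- A reader might infer a specific loss of sample size. That needs equal initiation rates in old and new enrollees, which the protocol does not state. The study is descriptive, and its size is set by the number of patients identified (Section 8.5).
- Prevalent UC in the abstract describes disease status, not registry status. A newly enrolled patient can have long-standing disease. The conflict with the abstract is only that it sets no enrolment date.

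**Conclusion.** The concern holds as a defect in the eligibility sentence. Section 8.2.2, as written, imposes an enrolment-date condition that conflicts with the abstract, with Sections 8.1, 8.2.3, 8.2.4, 8.5 and 8.9, and with its own allowance for earlier filgotinib users. If the condition is applied literally in ENEIDA, 76% to 83% of the 4-year UC census, or about 71% to 79% on the active-follow-up base, fails on enrolment date alone. This assumes that the stated annual enrolment continues for 4 years. How many initiators would be lost is unknown in all three registries. A selected, non-consecutive cohort would follow wherever the rule is applied, and the three registries could end up with different populations. The wording should be settled before cohorts are extracted.

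**What to change.** Reword Section 8.2.2 to take adults with UC who are registered in one of the three registries during the observational period (meeting its inclusion and consent requirements), whether first enrolled before or after 10 March 2023, and who initiate filgotinib after 10 March 2023 and within the observational period. Only the initiation is then dated. Registry membership during the study window should stay in the sentence, so that removing the enrolment date does not leave registration open-ended. State that the same rule applies in ENEIDA, ICC and SWIBREG.

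The cost is one sentence in a protocol amendment, with no new variables or data collection. If the sponsor does intend to restrict to new enrollees, the protocol should justify it, and the abstract and Sections 8.1, 8.5 and 8.9 should be changed to match.

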## 8.2.3. Exclusion Criteria

Patients who started filgotinib prior to the EC decision date without discontinuation until 10 March 2023 (= prevalent filgotinib users after the EC decision date) will be excluded.

## 8.2.4. Index Date, Follow-up

The index date (= start of follow-up) in each registry will be the date a patient starts UC treatment with filgotinib (i.e. the date of first identification of filgotinib exposure in the registry) after the EC decision date. The patient's total follow-up time is defined as the time from the filgotinib index date until the earliest of treatment discontinuation, study withdrawal (withdrawn from the registry, death or loss to follow-up) or end of study.

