*MACE* (i.e. fatal and nonfatal CVD events; CVD comprises coronary heart disease [angina, myocardial infarction], congestive heart failure, cerebrovascular disease and peripheral artery disease]): In patients 65 years of age and older, patients who are current or past long-time smokers, and patients with history of atherosclerotic CVD or other CV risk factors, filgotinib should only be used if no suitable treatment alternatives are available.

*VTE* (includes deep venous thrombosis) and pulmonary embolism [PE]): In patients with CV or malignancy risk factors filgotinib should only be used if no suitable treatment alternatives are available.

In patients with known VTE risk factors other than CV or malignancy risk factors, filgotinib should be used with caution. VTE risk factors other than CV or malignancy risk factors include previous VTE, patients undergoing major surgery, immobilization, use of combined hormonal

contraceptives or hormone replacement therapy, inherited coagulation disorder. Patients should be re-evaluated periodically during filgotinib treatment to assess for changes in VTE risk.

Patients with signs and symptoms of VTE should promptly be evaluated and filgotinib be discontinued in patients with suspected VTE, regardless of dose.

This longitudinal drug utilization study (DUS) is being conducted by the MAH as a Category 3 commitment to the EMA and to the Medicines and Healthcare products Regulatory Agency (MHRA) based on real-word secondary data derived from the same 3 IBD registries used for the filgotinib LTS PASS (GLPG0634-CL-413), namely the Estudio Nacional en Enfermedad Inflamatoria Intestinal sobre Determinantes Genéticos y Ambientales (ENEIDA) Register from Spain, the Initiative on Crohn and Colitis (ICC) Register from the Netherlands, and the Swedish National Quality Registry for Inflammatory Bowel Disease (SWIBREG).

This protocol follows the approach used in the already endorsed DUS for filgotinib in RA (GLPG0634-CL-408), thereby also taking into account prior comments from the PRAC Rapporteur.

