# 7. RESEARCH QUESTION AND OBJECTIVES

Information on prescribing of filgotinib for UC under real-world clinical practice is scarce, specifically, in the context of the updated prescribing information and HCP Guide after implementation of Article 20 decisions on JAKi's.

Therefore, this longitudinal DUS aims to describe physicians' adherence to the prescribing information of filgotinib in real-world clinical practice and to evaluate the effectiveness of the aRMMs by assessing how HCPs prescribing filgotinib adhere to the information provided in the SmPC in conjunction with the information in the HCP Guide with a specific focus on aRMMs implemented after the EC Article 20 decision on JAKi's (i.e. after 10 March 2023).

The objectives of this study are as follows:

- a. To describe the characteristics of patients treated with filgotinib in terms of:
- Demographics (e.g., age and sex)
- Comorbidities and prior and current medication use
- b. To evaluate prescribers' adherence to the filgotinib aRMMs, specifically:
- Compliance with the recommended posology (average daily dose) and duration of use
- Compliance with recommendations for patient screening and laboratory monitoring prior to and during treatment
- Compliance to recommendations for use in patients with moderate to severe chronic renal impairment/end stage renal disease or severe hepatic impairment
- Compliance with recommendations for limitations of use, including:
  - Use in patients with risk factors for venous thromboembolism (VTE)
  - Use in patients aged 65 years and older
  - Use in patients with risk factors for cardiovascular (CV) disease
  - Use in patients with risk factors for malignancy

- Use in patients with risk factors for serious infections
- Use in patients with concomitant use of other potent immunosuppressants
- Use of live attenuated vaccines
- Contraindicated use
- Compliance with discontinuation of filgotinib treatment in patients experiencing VTE

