## 8.3.2. Follow-up Variables

Follow-up variables assessed during filgotinib treatment will include (as per availability by each registry):

- Filgotinib maintenance dose and average daily dose
- Diagnosis of TB
  - Date of diagnosis
- Serious acute infection
  - Date of diagnosis
- Diagnosis of viral hepatitis
  - Date of diagnosis
- Diagnosis of herpes zoster
  - Date of diagnosis
- Pregnancy
  - Start of pregnancy
- Use of live-attenuated vaccines
- Laboratory monitoring of lipids (total cholesterol, high- and low-density lipoproteins [HDL, LDL], triglycerides) around 12 weeks after initiation of filgotinib treatment and thereafter
- Laboratory measurements (any time during follow-up)
  - ANC
  - ALC
  - Hb
- VTE event
  - Date of VTE diagnosis

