#### 8.4.2.4. Standardized Treatment Protocol

The following follow-up protocol is based on current standard of care. On the day of initiating therapy, the Week 0 visit will be filled out. The next visits reflect the minimum acquired visits in routine care and are scheduled on Week 12, Week 24, Week 52, and once yearly up to 10 years after initiation of treatment. If a patient or physician decides to discontinue the medication, the medication discontinuation form will be filled out and further registration is discontinued. All patients receive standard care and no additional questions, blood samples, interventions, questionnaires, or other activities have to be performed.

If a patient discontinues the medication and initiates another treatment that is included in the ICC Registry, the follow-up is again at Week 12, 24, 52, and 1 visit yearly.

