#### Follow-up

Among women starting filgotinib, the number and proportion who become pregnant during follow-up will be reported. Similarly, the number and proportion of patients who have a new

diagnosis of TB during follow-up, a serious acute infection, a diagnosis of viral hepatitis, concomitant treatment with other immunosuppressants, or who are administered a live attenuated vaccine will be reported. In patients with TB, or a serious infection identified during follow-up, it will be assessed whether treatment was stopped or interrupted after the diagnosis. The proportion of patients who have a test for lipids at around 12 weeks since initiation of filgotinib will be reported.

Should a VTE event occur, subsequent changes to filgotinib use will be reported (filgotinib treatment persistence or discontinuation).

Assessment of the filgotinib maintenance dose during follow-up will also be done in the subgroup of patients at high risk of MACE, VTE, or malignancy. In addition, the average daily dose during the maintenance period and the duration of use during the follow-up period will be reported.

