SmPC section 4.4: Special warnings and precautions for use: Infections			

Variable	Availability in individual registries yes/no (additional comments)		
	ENEIDA (ES)	ICC (NL)	SWIBREG (SE)
Acute infection	no (only serious or opportunistic infection can be recorded)	yes	yes (NPR, PDR [prescription of antibiotics])
Dx of acute infection	no	yes	yes (NPR, PDR)
SmPC section 4.4: Special warnings and precautions for use: Viral reactivation	yes (if not available, might be in medical report)		
Viral hepatitis	yes (if not available, might be in medical report)	yes	yes (NPR)
Dx date of viral hepatitis	yes	yes	yes (NPR)
Herpes zoster (HZ)	yes (if not available, might be in medical report)	yes	yes (NPR)
Dx date of HZ	yes	yes	yes (NPR)
SmPC section 4.4: Special warnings and precautions for use: Lipids			
Laboratory measurement of total cholesterol	no (might be in medical report)	no (but will be added)	no
Date of measurement	no (might be in medical report)	(at baseline, week 0), and at follow-up week 12,24, 52 and the year 1, 2, 3)	
Laboratory measurement of HDL	no (might be in medical report)	no (but will be added)	no
Date of measurement	no (might be in medical report)	(at baseline, week 0), and at follow-up week 12,24, 52 and the year 1, 2, 3)	no

Variable	Availability in individual registries yes/no (additional comments)		
	ENEIDA (ES)	ICC (NL)	SWIBREG (SE)
Laboratory measurement of LDL	no (might be in medical report)	no (but will be added)	no
Date of measurement	no (might be in medical report)	(at baseline, week 0), and at follow-up week 12,24, 52 and the year 1, 2, 3)	no
Laboratory measurement of triglycerides	no (might be in medical report)	no (but will be added)	no
Date of measurement	no (might be in medical report)	(at baseline, week 0), and at follow-up week 12,24, 52 and the year 1, 2, 3)	no
Laboratory measurement of HDL:LDL	no (might be in medical report)	no (but will be added)	no
Date of measurement	no (might be in medical report)	(at baseline, week 0), and at follow-up week 12,24, 52 and the year 1, 2, 3)	no
SmPC section 4.4: Special warnings and precautions for use: Haematological abnormalities			
Same as for baseline assessment	no (might be in medical report)	yes	yes (currently for <20%)
SmPC section 4.4: Special warnings and precautions for use: VTE			
VTE event during FU (including PE and deep vein thrombosis)	yes (if not available, might be in medical report)	yes	yes (NPR)
Dx date of VTE	yes	yes	yes (NPR)

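### Ending follow-up at treatment discontinuation drops VTEs recorded after a stop made on suspicion, which biases measured compliance with stopping for VTE downward, mainly in ENEIDA and ICC

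*Protocol*

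**What the plan says.** Section 8.2.4 defines total follow-up as running from the index date "until the earliest of treatment discontinuation, study withdrawal (withdrawn from the registry, death or loss to follow-up) or end of study". Section 8.3.2 lists the VTE event and its date under this lead-in: "Follow-up variables assessed during filgotinib treatment will include (as per availability by each registry". Annex 3, Table 5 names the variable "VTE event during FU (including PE and deep vein thrombosis". No section gives an observation window after the stop.

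The recommendation whose uptake is measured is in Section 6: "Patients with signs and symptoms of VTE should promptly be evaluated and filgotinib be discontinued in patients with suspected VTE, regardless of dose". Section 7 makes it an objective: "Compliance with discontinuation of filgotinib treatment in patients experiencing VTE". Section 8.7 (Follow-up) says how it will be reported: "Should a VTE event occur, subsequent changes to filgotinib use will be reported (filgotinib treatment persistence or discontinuation".

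The registries define the end of exposure differently. ENEIDA and ICC use recorded start and stop dates (Sections 8.3.3.1 and 8.3.3.2). In ICC, after a stop, "the medication discontinuation form will be filled out and further registration is discontinued", unless the patient starts another treatment covered by that registry (Section 8.4.2.4). SWIBREG counts each dispensing as 180 days of exposure (Section 8.3.3.3), although Table 5 also lists a discontinuation date from SWIBREG itself.

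**The concern.** A prescriber who follows the recommendation acts on suspicion, so the stop can be dated before the VTE is confirmed and recorded. Under Sections 8.2.4 and 8.3.2 that VTE then lies outside follow-up. Even if it were retrieved, Section 8.7 looks only at changes after the event and has no rule for a stop that precedes it. A VTE in a patient who stays on filgotinib is always inside follow-up.

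Entry to the denominator therefore depends on the behaviour being measured, and every case lost in this way is a compliant one. At stake is one named adherence objective, which would look worse than practice really is. Few VTEs are likely, so one or two lost cases can move the proportion visibly.

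**Working it through.** No figure in the protocol depends on the follow-up definition, so there is none to reproduce on this point. As a background check, the study-size figures in Section 8.5 do reproduce: for 10% in 300 patients, √(0.1 × 0.9/300) = 1.73%, with a 95% CI of 6.6% to 13.4%.

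**Inputs**
- From the protocol: the end of follow-up (8.2.4), ascertainment on treatment only (8.3.2), the stop at suspicion (6), and reporting of later changes only (8.7).
- Assumed, because the protocol does not give them: c, the share of VTE patients whose filgotinib is stopped because of the VTE; f, the share of those stops dated before the recorded diagnosis; and the VTE risk.

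**Derivation**, where recorded stop dates end follow-up
- Of all VTE patients, a share cf is compliant but lost.
- Compliant and still counted: c − cf = c(1−f).
- Counted in total: 1 − cf.
- Observed compliance: c(1−f)/(1−cf).
- Observed minus true: −cf(1−c)/(1−cf). This is negative whenever 0 < c < 1 and f > 0.

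**Observed compliance** (fall in percentage points in brackets)

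| True c | f = 0.10 | f = 0.25 | f = 0.50 | f = 0.75 |
|---|---|---|---|---|
| 0.70 | 68% (2) | 64% (6) | 54% (16) | 37% (33) |
| 0.80 | 78% (2) | 75% (5) | 67% (13) | 50% (30) |
| 0.90 | 89% (1) | 87% (3) | 82% (8) | 69% (21) |

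In whole cases: of 10 VTEs, 8 are managed by stopping. If 4 of the 8 stops precede the recorded diagnosis, the result is 4/6 = 67% against a true 80%, and 40% of the VTEs are missing. If 6 precede it, the result is 2/4 = 50%. If c = 1 the proportion is unbiased, but cases are still lost.

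**Number of events.** At assumed VTE risks of 0.5% to 2%, 500 patients give 500 × 0.005 = 2.5 to 500 × 0.02 = 10 VTEs.

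**SWIBREG.** With 180 days credited per dispensing, a VTE coded shortly after the real stop usually still falls inside derived exposure and is counted. The derived end can, however, lie well after the real stop, so prompt stopping may be read as persistence. That also lowers measured compliance, by a different route. If the SWIBREG-recorded discontinuation date were used instead, the mechanism above would apply.

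**The case against.** The strongest reply is that the effect is narrower than it first looks, and much of that reply stands.

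- **Not every compliant case is lost.** A reader might infer that compliant cases vanish and only non-compliant ones remain. Only stops dated before the recorded diagnosis are lost. Later stops are kept, and same-day stops depend on a boundary rule that is not stated.
- **The registries differ.** A reader might infer one mechanism in all three. Section 8.3.3.3 does not support that for SWIBREG.
- **TB and serious infection.** A reader might infer the same flaw in the analysis of stopping after these diagnoses. The same ordering of dates is possible but not shown: the protocol states a stop at suspicion only for VTE. Telling interruption from discontinuation does need re-start data after the stop. It can be argued that an interrupted patient has not reached the end point in Section 8.2.4, and SWIBREG's retrospective linkage can show later dispensings.
- **The size is not established.** At f = 0.10, 80% becomes 78% and 90% becomes 89%.
- **The weight is limited.** The study is descriptive, without hypotheses. Stopping for VTE is one objective among many, and long-term safety has its own study in the same registries, so understated event counts matter less here.

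The reply does not remove the core. Section 8.7 lets the SAP modify the analysis, but the follow-up end and the observation window are fixed in the protocol. In ICC an analysis plan cannot recover data that were not recorded after the stop. Section 8.1 speaks of follow-up until dropout, but leaves that term undefined and does not override Section 8.2.4.

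**Conclusion.** The point holds for VTE, mainly in ENEIDA and ICC. The follow-up definition excludes compliant stops dated before the recorded diagnosis, and no other section repairs this. The direction is downward whenever some but not all VTE patients are stopped because of the VTE and some of those stops precede the recorded date. The size is unknown: about 1 to 33 percentage points over the assumed ranges for c and f, neither of which the protocol supplies. In SWIBREG the likely problem is a prompt stop misread as persistence. The documents do not support treating TB and serious infection as shown to be affected, or quoting any one figure as the expected bias. This should be fixed, but it does not undermine the study's other objectives.

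**What to change.** - **Sections 8.2.4 and 8.3.2:** keep discontinuation as the end of exposure. Continue ascertaining VTE (and, for consistency, TB and serious infection) for a fixed, prespecified window after the recorded stop date.
- **SWIBREG:** anchor the window on the SWIBREG-recorded discontinuation date where available, and add no further window after the 180-day derived end. A 30-day window added there, for example, would reach 180 + 30 = 210 days after a dispensing.
- **Section 8.7:** count a stop as compliant if it falls in a prespecified interval spanning the diagnosis date. Report separately stops with another recorded reason, such as lack of efficacy. Otherwise a stop unrelated to a later VTE would be credited as compliance and push the estimate upward. Record re-starts so that interruption can be told from discontinuation.
- **ICC:** capture any such event at the existing discontinuation form. The form's content is not shown, so an added item may or may not be needed.

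The cost is mainly protocol wording. SWIBREG already links to dated events. Some ENEIDA events depend on chart abstraction, which needs study-specific consent. A few events and stops unrelated to each other may be included. The change concerns measurement only and alters no clinical rule.
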